### Annual Safety Report (ASR):

In addition to the expedited reporting, the sponsor shall submit an annual report **once a year** or on request throughout the clinical trial period, according to section 13, para. 6 GCP-V.

## **11 Documentation**

It is the reasonability of the investigator to perform the clinical study in accordance with the GCP guidelines, the AMG, and the clinical study protocol. All data have to be recorded correctly in the

CRF by authorized persons only. This also includes data of persons that were excluded from the clinical study.

The investigator records the participation of a person at the Participant Identification Log (PIL). This list is meant to identify participating persons at a later point of time. It includes the complete name, the date of birth, and the date of inclusion into the clinical study. The PIL remains in the study centre after the study is finished. In addition, participation in the clinical study has to be recorded in the patient's chart (including study medication, participant number/randomization number, start and end of the clinical study).

It has to be ensured that the person responsible for documentation in the CRF can be identified. Therefore, a list with signatures and abbreviations (site signature log) is kept in the ISF and in the TMF.

## 11.1 Case report form (CRF)

All data of the participants have to be recorded in the Case Report Forms exclusively designed for the study.

The Case Report Forms are to be filled in only with a **black ballpoint pen**. Corrections are to be conducted in a way, that the original entry stays visible (the use of correcting fluids is not allowed). Corrections have to be signed and dated by the authorized person that has carried them out. Data, that are not available or have not been collected, have to be clearly identified as such (NA or ND). If necessary the reasons should be documented.

The Investigator is responsible for all data of the participant to be documented in the case report form immediately, readably, correctly and according to the patient's chart.

When plausibility and completeness of the CRFs have been verified by the monitor, the original CRFs are sent to SAL-Studienzentrale, a copy stays at the site and has to be stored for 10 years.

## 11.2 Investigator Site File

The SAL-Studienzentrale Dresden provides the Investigator Site File to the study centre. The ISF includes all documents that are required for the clinical study. During monitoring, the ISF will be checked regularly for completeness and actuality. After the clinical trial is finished or stopped, the ISF has to be stored for 15 years.

## 11.3 Data Storage

### 11.3.1 Responsibilities of the Sponsor

As required by law, all important study documents have to be stored by the sponsor for at least 10 years after the clinical trial was finished or stopped.

### 11.3.2 Responsibilities of the Investigator

All documents that are related to the clinical study and to the distribution of the study medication (e.g. CRFs, written informed consent forms, study medication lists and other relevant material) have to be stored for at least 10 years.

Source data like patients' charts, laboratory analyses, and other original data have to be stored for the longest possible time that is usual practice at the investigator's site.

## 11.4 Data entry and data management

Data management is performed by SAL-Studienzentrale by means of study software MACRO 3.0. Data are proven by programmed range checks, validity checks, and consistency checks. In addition, a manual/visual data check for medicinal plausibility is done according to GCP guidelines. There might be discrepancies that are to be clarified by means of special forms sent to the investigator's site.

After being filled in by the investigator the query forms are sent back to the data management, where the discrepancies are corrected in the data bank. The query forms are stored together with the CRFs both at the investigator's site and at the data management site.

After the study is finished and before data are analysed, a blinded meeting will be held between the sponsor and statistician. When the database has been declared to be complete and accurate, it will be locked. This procedure has to be documented.

## **12 Quality Assurance System**

During the clinical trial, quality control and quality assurance will be ensured through monitoring, auditing and supervision by the authorities.

## 12.1 Quality Control (Monitoring)

The study will be monitored to verify that

- the rights and well-being of the trial subjects are protected,
- the reported trial data are accurate, complete and verifiable from source documents.
- the conduct of the clinical trial is in compliance with the currently approved protocol / the currently approved protocol amendment(s), with ICH-GCP and with applicable regulatory requirements.

The investigator will grant the monitor access to the subjects' personal medical records for the verification of the proper documentation of study data. The provisions of the Federal Data Protection Act will be fully observed (the monitor is bound by medical secrecy when comparing the CRFs with the source documents).

All investigators agree that the monitor will visit the centre during and after completion of the study. The investigator must allow sufficient time for these visits, alternatively the monitor may be provided with other trained staff (e.g. so-called co-investigators) for assistance during the visits. The investigator will grant the monitor access to the source documents for the fulfilment of his/her duty.

A monitoring report will be written on each visit. This will document the progress of the clinical trial and give an account of all problems that occurred (e.g. refusal of inspection).

### 12.2 Source Data Verification (SDV)

Source data verification will be performed in order to verify the accuracy and completeness of the entries on the case report form (CRF) by comparing them with the source data, and to ensure and increase the quality of the data. All data which are subject to SDV must have been entered in the medical record or, in the case of source documents, enclosed with the medical record. The investigators will afford the CRA access to the medical records for the performance of SDV.

Source data as defined by ICH-GCP include data such as hospital records, clinical and office charts, laboratory notes, memoranda, subjects' diaries or evaluation checklists, pharmacy dispensing records, recorded data from automated instruments, copies or transcriptions certified after verification as being accurate copies, microfiches, photographic negatives, microfilm or magnetic media, x-rays, and records kept at the pharmacy, at the laboratories and at medico-technical departments involved in the clinical trial.

### 12.3 Quality Assurance (Auditing)

According to the ICH-GCP guidelines, audits may be performed according to a quality assurance system. These may be conducted by the sponsor.

## **13 Biostatistical Planning and Analysis**

#### 13.1 Study Design

This trial is designed as a single arm multicentre phase IIa study. The results of the primary endpoint will be compared with historical data from patients with same clinical characteristics. See also section 2.1. The main reason for a one-arm non-randomised design is the rarity of the disease which would cause a very long accrual period in case of a two-arm randomised design. Since the prognosis of the targeted patient population is considerably reduced by the c-KIT or FLT3 mutations, results on midostaurin efficacy should be available within a time period under 10 years. Given the fact that there are various available publications on historical cohorts, it seems justifiable to set up a single-arm study.

## 13.2 Target Variable/Endpoints

## 13.2.1 Primary Target Variable

As pointed out in section 2.1, the reduction of overall survival in patients with c-KITmut is mainly due to a higher incidence of relapses while in FLT3-ITD patients, primary resistant disease leads to the inferior prognosis during the early course of the disease. Since the patient group in this trial consists both of c-KITmut and FLT3-ITD patients, event-free survival seems to be the measure to capture both early treatment failure in FLT3-ITD and later relapse from CR in c-KITmut patients. Therefore, the primary study endpoint will be event-free survival (EFS).

Event-free survival rate at 2 years is defined as the time from study inclusion (date of informed consent) until either primary treatment failure or hematologic relapse or death from any cause occurs. Primary treatment failure is defined as the absence of CR/CRi five weeks (35 days) after the start of MidoDA induction treatment.

## 13.2.2 Secondary Target Variables

- Overall survival = Time from study inclusion (date of informed consent) until death from any cause occurs
- Relapse-free survival = time from documented CR until either relapse or death from any cause, whichever event occurs first
- Time to relapse = Time from study inclusion (date of informed consent) until hematologic relapse
- Toxicity = incidence of AEs
- MRD kinetics = quantitative values of molecular or flow-cytometric disease markers over time

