#### **MidoDA**

Cytarabine	100 mg/m  IV over 24 hrs	days 1-7
Daunorubicine	60 mg/m  IV over 1 hr	days 3-5
Midostaurin	50 mg/m  (2 capsules) p.o. twice daily	days 8-21

Midostaurin 50 mg (two 25 mg capsules) is given twice a day by mouth on days 8-21. Patients should take their doses at approximately the same time each day, and approximately 12 hours should elapse between the morning and evening doses. Each daily dose should be given with food and a glass of water (approx. 240 ml). Patients should be instructed to swallow capsules whole and not chew capsules. If vomiting occurs, no re-dosing is allowed before the next scheduled dose.

For **response assessment**, a bone marrow aspirate (or bone marrow biopsy) must be performed one week after recovery of ANC  $\geq$  1000/µL and platelets  $\geq$  100,000/µL to document a complete remission. Remission assessment must be performed latest 35 days after the beginning of second induction, even if ANC or platelets are below the described threshold.

If response assessment shows < 5% myeloid blasts, the patient has achieved a CR/CRi and will continue consolidation treatment according to this protocol.

If response assessment reveals  $\geq$  5% myeloid blasts, the patient will be classified as primary refractory disease and will discontinue study treatment. Patients who discontinue study treatment will be followed up until 25 months after study entry.

At each bone marrow aspiration, material should be obtained and sent to the central SAL laboratory in Dresden for MRD diagnostics (see section 7.4).

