### **MidoHiDAC**

Cytarabine	3000 mg/m  IV over 3 hrs twice daily	days 1,3,5
Midostaurin	50 mg (2 capsules) p.o. twice daily	days 8-21

High-dose cytarabine (HiDAC) 3000 mg/m^2 will be given by intravenous infusion over 3 hours every 12 hours on days 1, 3, and 5. Serial neurologic evaluation will be performed before and following the infusion of high-dose cytarabine.

It is recommended to administer dexamethasone 0.1% or other corticosteroid ophthalmic solution 2 drops to each eye four times per day to begin 6-12 hours prior to the initiation of the cytarabine infusion and to continue for at least 24 hours after the last cytarbine dose.

Midostaurin 50 mg (two 25 mg capsules) is given twice a day by mouth on days 8-21. Midostaurin is not given from day 22 of the current cycle and day 7 of the next consolidation cycle. Patients should take their doses at approximately the same time each day, and approximately 12 hours should elapse between the morning and evening doses. Each daily dose should be given with food and a glass of water (approx. 240 ml). Patients should be instructed to swallow capsules whole and not chew capsules. If vomiting occurs, no re-dosing is allowed before the next scheduled dose.

For **remission assessment**, a bone marrow aspirate (or bone marrow biopsy) must be performed one week after recovery of ANC  $\geq$  1000/µL and platelets  $\geq$  100,000/µL to document a complete remission. Remission assessment must be performed latest 35 days after the beginning of each consolidation cycle, even if ANC or platelets are below the described threshold.

If remission assessment shows < 5% myeloid blasts, the patient has a sustained CR/CRi and will continue treatment according to this protocol.

If remission assessment reveals  $\geq$  5% myeloid blasts, the patient has a relapse from CR/CRi and will discontinue study treatment. Patients who discontinue study treatment will be followed up until 25 months after study entry.

At each bone marrow aspiration, material should be obtained and sent to the central SAL laboratory in Dresden for MRD diagnostics (see section 7.4).

Three cycles of MidoHiDAC shall be administered depending on adequate blood counts and sufficient organ function.

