### 9.1.2 Complete Response with incomplete blood count recovery (CRi):

CRi satisfies all CR criteria except platelet counts are < 100,000/µL or ANC < 1,000/µL

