#### 9.1.3 Relapse

### Any of the following, occurring after either CR or (CRi):

- The reappearance of circulating blast cells on more than one determination
- >5% AML blasts in the bone marrow, not attributable no another cause (e.g. bone marrow regeneration). If there are no circulating blasts, but the marrow contains 5%-20% blasts, a repeat marrow ≥ 1 week later with >5% blasts is necessary to meet the criteria for relapse.
- Development of extramedullary leukemia

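### Relapse-free survival starts at documented CR only, although the protocol's failure, relapse and continuation rules use CR or CRi, so a patient who stays in CRi has no start date

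*Protocol*

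**What the plan says.** Section 13.2.2 of the protocol lists the secondary target variables, among them "Relapse-free survival = time from documented CR until either relapse or death from any cause, whichever event occurs first".

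Section 9.1 separates two kinds of remission. CR (9.1.1) requires, among other things, ANC of at least 1000/µL and platelets of at least 100,000/µL. CRi is a category of its own (9.1.2): "CRi satisfies all CR criteria except platelet counts are" below 100,000/µL or ANC is below 1,000/µL.

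Other rules accept either category:

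- **Primary failure (13.2.1):** "Primary treatment failure is defined as the absence of CR/CRi five weeks (35 days) after the start of MidoDA induction treatment". Sections 6.3 and 9.1 say the same, and both count relapse from CR/CRi as an event.
- **Relapse (9.1.3):** the definition opens "Any of the following, occurring after either CR or (CRi" and then lists the criteria.
- **After second induction (7.1, MidoDA):** with fewer than 5% myeloid blasts, "the patient has achieved a CR/CRi and will continue consolidation treatment according to this protocol".
- **After each consolidation (7.1, MidoHiDAC):** with the same blast result, "the patient has a sustained CR/CRi and will continue treatment according to this protocol".

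On timing, section 7.1 states "Remission assessment must be performed latest 35 days after the beginning of second induction, even if ANC or platelets are below the described threshold".

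**The concern.** An endpoint that runs from remission to relapse or death needs an origin for every patient in whom the protocol can declare a relapse. Here relapse is defined after CR or CRi, while the clock is started by CR alone. Two groups are affected:

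- **CRi throughout.** The patient is a responder, continues treatment and can relapse under 9.1.3, but has no date from which RFS can be measured.
- **CRi first, CR later.** The clock starts at the later date. A patient who relapses or dies in between never enters, so those who do enter have been selected for staying relapse-free up to that point.

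What is at stake is which patients the RFS estimate describes. The text names responders, but would deliver only those responders whose counts recovered. In a trial of 18 patients, leaving out one or two is visible in the estimate.

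**Working it through.** **1. The plan's own figure.** The protocol states no number for RFS. Its only design figure concerns 2-year EFS (13.3): p0 = 0.5, p1 = 0.8, N = 18, and rejection with 13 or more event-free patients. By the exact binomial:

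- P(X ≥ 13 | n = 18, p = 0.5) = 0.0481, within the stated 5%
- P(X ≥ 13 | n = 18, p = 0.8) = 0.867, above the stated 80%

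The design reproduces. EFS already treats CRi as response, so nothing below changes it.

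**2. The rules side by side.**

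| Rule | Section | Remission state used |
|---|---|---|
| Primary failure | 6.3, 9.1, 13.2.1 | absence of CR/CRi |
| EFS relapse event | 9.1 (also 6.3) | relapse from CR/CRi |
| Relapse definition | 9.1.3 | after CR or CRi |
| Continue to and through consolidation | 7.1 | CR/CRi |
| Time to relapse, origin | 13.2.2 | none needed (runs from consent) |
| RFS, origin | 13.2.2 | CR only |

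For a patient who stays in CRi and then relapses, this gives an EFS event, a time-to-relapse event and no RFS record.

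**3. Are such patients foreseeable?** Yes, for two reasons in section 7.1.

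- The remission marrow is normally taken one week after count recovery, but day 35 is the latest date, "even if ANC or platelets are below the described threshold". A patient assessed at that limit with low counts and fewer than 5% blasts can be CRi but not CR.
- Consolidation and maintenance may begin at platelets of at least 50,000/µL, whereas CR needs 100,000/µL. A patient between the two values can stay on treatment without meeting the CR platelet criterion.

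**4. How many patients?** The protocol gives no CRi rate. Assume, for illustration only, 14 to 18 responders with 10% to 40% of them never progressing from CRi to CR.

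- Fewest without an origin: 14 × 0.10 = 1.4. Most: 18 × 0.40 = 7.2.
- Fewest left in RFS: 14 × 0.60 = 8.4. Most: 18 × 0.90 = 16.2.

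So about 1 to 7 responders would be missing and about 8 to 16 analysed. With the origin at CR or CRi, all 14 to 18 are analysed.

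**5. How much would the RFS rate move?** Let m be the number of responders, k those in CRi only, and d the 2-year RFS after CR minus that after CRi. Then

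RFS(CR only) − RFS(all responders) = (k/m) × d.

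Take m = 16 (assumed):

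| k | d = 0 | d = 0.25 (75% against 50%, assumed) |
|---|---|---|
| 2 | 0 | 2/16 × 0.25 = 3.1 points |
| 4 | 0 | 4/16 × 0.25 = 6.3 points |
| 6 | 0 | 6/16 × 0.25 = 9.4 points |

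If d were negative, the sign would reverse. The protocol gives no value for d, so the table shows how the result depends on it and does not estimate a bias.

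**6. Late entry.** If CRi is documented at t1, CR at t2 and relapse occurs at T, the literal RFS is T − t2 instead of T − t1. The interval t2 − t1 is not credited, which shortens that patient's RFS, while patients who fail between t1 and t2 are left out. The two effects pull in opposite directions, and the document does not allow the net effect to be worked out.

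**The case against.** The strongest reply is that the protocol uses CR loosely and that the RFS line is one more case. This is partly right. Section 4.3 sends patients on to consolidation after complete remission is confirmed, where section 7.1 says CR/CRi. Section 7.1 describes the marrow examination as documenting a complete remission, yet classifies the result as CR/CRi. It offers maintenance to patients in continuing complete remission while allowing a platelet count below the CR threshold. Section 13.2.1 speaks of relapse from CR when explaining the choice of EFS. A reader might therefore infer that RFS is the only place where CR stands alone; it is not. The intended origin may well have been CR or CRi. That does not settle the endpoint, however: CR and CRi are defined separately, and no passage says that CR in 13.2.2 includes CRi.

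It can also be said that a CR-only origin was deliberate, since section 9.1 adopts the revised IWG criteria. The document alone cannot exclude this. If so, the protocol would still have to say what happens to CRi patients, because it defines relapse for them.

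Nor can the matter be left to the analysis plan. The protocol fixes the origin itself, so a plan using CR or CRi would depart from it.

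The consequence is small, and this objection stands. RFS has no hypothesis, threshold or decision rule. A relapse or death from CRi is counted in EFS, and a relapse also in time to relapse, so no relapse would go unreported.

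**Conclusion.** Wrong as written, as an internal inconsistency. It is minor and confined to a secondary endpoint. On the literal text, a CRi-only responder has no RFS origin, and a patient who reaches CR late enters only if still relapse-free. This rests on the protocol's own definitions and needs no assumption. The number of patients affected does need one, because no CRi rate is given; what is certain is that each CRi-only patient removes one responder from an analysis of at most 18.

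Three stronger readings are not supported:

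- **That RFS will be overstated by some 3 to 9 points.** That range follows entirely from an assumed 25-point difference in outcome between CR and CRi. Nothing in the protocol says CRi patients do worse, and with equal outcomes the difference is zero.
- **That disagreement between RFS and EFS is itself a fault.** EFS runs from consent in all patients and RFS from remission in responders. They differ by construction and would still differ after the correction.
- **That the trial's main conclusion is at risk.** The EFS endpoint, N = 18 and the 13-of-18 rule are untouched.

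**What to change.** In section 13.2.2, define RFS as running from the first documentation of CR or CRi to hematologic relapse under section 9.1.3 or death from any cause, whichever is earlier. RFS from CR alone may be shown as a descriptive subset. If a CR-only origin was intended, say so and state how patients in CRi are handled.

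The cost is one sentence of wording. No data, visits or treatment rules change, because remission status is already assessed after second induction and after each consolidation cycle. The drawback for the sponsor is that the reported RFS may be slightly less favourable if CRi patients do worse.

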## **13.3 Sample Size Calculation**

The primary endpoint is a binary variable indicating event-free-survival at 2 years. The reference 2year-EFS rate was obtained from data of the SAL study group including 104 patients with t(8;21). Of the 104 patients, 78 did neither display FLT3-ITD nor c-KITmut. Eight patients were FLT3-ITD positive and 18 patients displayed a c-KIT mutation.

Reference 2-year-EFS rate of a historical cohort: p0 = 0.5Success rate of interest: p1 = 0.8Difference between reference and success rate of interest:  $\delta = 0.3$ nullhypothesis:  $p \le p0$ alternate hypothesis:  $p \ge p1$ power: 80% significance level: 5% one sided The nullhypothesis of this trial is that the 2-year-EFS rate is worse or equal to 0.5 under the experimental treatment. The alternate hypothesis is that the 2-year-EFS-rate is equal to 0.8 or greater. In an exact single stage phase 2 design 18 patients have to be enrolled to be able to detect the critical difference in the EFS-rates of 0.3 with a power of 80% and a one-sided significance level of 5%. The nullyhpothesis can be rejected if after 2 years 13 or more of 18 patients are without an event. The calculation is based on the exact binomial distribution as described in A'Hern [27].

### **13.4 Definition of Populations Included In the Analyses**

All patients included will be analysed. Patients whose 2-year-EFS status cannot be evaluated will be excluded from the primary analysis. Worst case and best case analyses including these patients will be conducted as sensitivity analyses.

